8.2.5 PROMIS Scales

The PROMIS Short-Form Fatigue, Sleep Disturbance, and Cognitive Function – Abilities Scale Instruments each consist of 8 items in which responses are scored 1 to 5 for each item. Scores for all items are totaled to create a raw score. Each instrument will be considered invalid if 50% of the items are missing. If more than 50% of the items are answered, the raw total score will use the following formula to determine a new calculated score to account for missing items.

$$\text{New raw score} = (\text{Raw score} / \# \text{ of items answered}) \times \# \text{ of total items}$$

New raw scores that are fractions are rounded up to the nearest whole number. Once a new raw score has been calculated, a T-score will be determined using [Appendix A](#) for Fatigue Inventory, [Appendix B](#) for Sleep Disturbance and [Appendix C](#) for Cognitive Function – Abilities scale. The T-scores will be analyzed.

Note that items 1, 2, and 8 of the PROMIS Sleep Disturbance Instrument will need to have their directionality reversed for calculating the totals.

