^f There will be a thorough examination (visual and palpation) of the oral cavity at the Screening Visit and then visual examinations at all other in-clinic visits. For visits at which a visual exam is not possible (ie, telephone visit), the visual oral cavity exam is not required; in lieu of the in-clinic (or home visit) oral cavity exam, after conclusion of “any changes in your medical condition”, ask specifically if there have been any changes or problems in the oral cavity. Patients reporting any concerning lesion description or painful processes in the oral cavity possibly related to study drug exposure should be strongly urged to come into clinic for an Unscheduled Visit for oral cavity exam. In circumstances in which, due to the COVID-19 pandemic, it is not possible for the patient to return to the clinic for the Unscheduled Visit exam, a clinician certified by the Sponsor to conduct oral cavity examination should contact the patient by phone and obtain greater history and description of the oral cavity AE by patient, potentially augmented with images of oral cavity taken by the patient and sent to the site for the examining clinician to textually document in the source. In addition to the regularly scheduled in-clinic examinations, an unscheduled examination of the oral cavity in-clinic should be performed any time a patient contacts the clinic to report an oral cavity lesion or other oral AE possibly related to study drug exposure, other than oral numbness, tingling, or noticeable taste (eg, bitter, metallic, or unpleasant) after dosing, which do not require unscheduled examinations.

^g The Screening version of the mMBM will be administered.

^h The Baseline/Post-Randomization version of the mMBM will be administered.

ⁱ For telephone visits, the patient will be mailed all applicable patient reported outcomes for a given visit.

^j Weekly recall of daily average Long COVID pain intensity on the NRS scale is required at the Screening Visit. Patients should only continue screening if they score ≥ 4 and ≤ 9 .

^k Clinical laboratory tests will be performed at Screening, Week 6, Week 14/ET. TSH, ESR, and HbA1c will be tested at Screening only.

^l Human immunodeficiency virus (HIV), hepatitis C virus (HCV) and hepatitis B surface antigen (HBsAg) testing will be performed at Screening and may be performed at other visits, at the discretion of the Investigator or Sponsor. Medical Monitor approval is required for repeat testing.

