(Telephone visit exception: visual exam of the oral cavity is not required – but in addition to standard inquiry about AEs, site staff will inquire specifically if there have been any changes or problems in the oral cavity. Patients reporting any concerning lesion description or painful processes in the oral cavity possibly related to study drug exposure should be strongly urged to come into the clinic for an Unscheduled Visit for oral cavity exam. In circumstances in which, due to the COVID-19 pandemic, it is not possible for the patient to return to the clinic for the Unscheduled Visit exam, a clinician certified by the Sponsor to conduct oral cavity examination should contact the patient by phone and obtain greater history and description of the oral cavity AE by patient, potentially augmented with images of oral cavity taken by the patient and sent to the site for the examining clinician to *textually* document in the oral exam source document.)

- Administer Baseline/Post-Randomization Version of mMBM
- Administer the “Since Last Visit” version of the C-SSRS. (Telephone visit exception: C-SSRS is administered over the phone).
- Patient should complete the following PROs (Telephone visit exception: all PROs should be mailed ahead of the visit and returned to the clinic after completion via courier):
 - a. SDS
 - b. PROMIS Short Form – Sleep Disturbance
 - c. PROMIS Short Form v1.0 – Fatigue 8a
 - d. PROMIS Short Form v1.0 – Cognitive Function - Abilities
 - e. PGI-C
 - f. PCFS
 - g. ISI
 - h. ESS
- Clinical laboratory tests, including serum chemistry, hematology, urinalysis. (Telephone visit exception: laboratory tests are not required).
- Administer urine pregnancy test for females of child-bearing potential (processed in-clinic). (Telephone visit exception: urine pregnancy test will be performed at home by patient for women of child-bearing potential).
- Record vital signs (Telephone visit exception: vital signs are not required).
- Assessment of eDiary compliance of 24-hour recall of worst Long COVID pain and sleep quality. Discuss any compliance concerns with the patient and provide re-training as needed.

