17.4. Case Report Forms (CRFs)

The Investigator is required to prepare and maintain adequate and accurate case histories designed to record all observations and other data pertinent to the study for each study patient. Data must be recorded on CRFs approved by Tonix or its designee. Data (including AEs) will be recorded on raw data sheets and/or electronic or paper source documents.

If selected data are collected via paper (patient questionnaires, etc.), the data must be entered into the CRF and verified that it has been transcribed correctly.

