Appendix 7: PROMIS – Sleep Disturbance Scale

PROMIS® Item Bank v1.0 – Sleep Disturbance – Short Form 8a

Sleep Disturbance – Short Form 8a**Please respond to each question or statement by marking one box per row.**

In the past 7 days...		Very poor	Poor	Fair	Good	Very good
Sleep109	My sleep quality was	 5	 4	 3	 2	 1
In the past 7 days...		Not at all	A little bit	Somewhat	Quite a bit	Very much
Sleep116	My sleep was refreshing.	 5	 4	 3	 2	 1
Sleep20	I had a problem with my sleep	 1	 2	 3	 4	 5
Sleep44	I had difficulty falling asleep	 1	 2	 3	 4	 5
Sleep108	My sleep was restless	 1	 2	 3	 4	 5
Sleep72	I tried hard to get to sleep	 1	 2	 3	 4	 5
Sleep67	I worried about not being able to fall asleep	 1	 2	 3	 4	 5
Sleep115	I was satisfied with my sleep.	 5	 4	 3	 2	 1

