15.5 Appendix E

The following list of numbers will be used for random seeds where required for MI processes:

4892962

3752934

5798332

3796594

6437925

3949255

[figure not shown]
3597909

3067243

7256068

6953553

[figure not shown]
These will generally be used in order for the primary analysis, then secondary endpoints and sensitivity analyses. For cases where identical code may be applied to more than one outcome or a sensitivity analysis that uses a minor variation on the primary code, the second to last digit will be incremented by 1 to produce new seeds for the subsequent outcome/analysis. If a single dataset requires more than the 10 seeds above, additional seeds will be generated by incrementing the last digit in the last by 1. All seeds used will be documented in the programming specifications and the programs themselves.

Intermediary Delivery Events

Status

Timestamp

ELECTRONIC RECORD AND SIGNATURE DISCLOSURE

From time to time, Rho, Inc. (we, us or Company) may be required by law to provide to you certain written notices or disclosures. Described below are the terms and conditions for providing to you such notices and disclosures electronically through the DocuSign system. Please read the information below carefully and thoroughly, and if you can access this information electronically to your satisfaction and agree to this Electronic Record and Signature Disclosure (ERSD), please confirm your agreement by selecting the check-box next to 'I agree to use electronic records and signatures' before clicking 'CONTINUE' within the DocuSign system.

Getting paper copies

At any time, you may request from us a paper copy of any record provided or made available electronically to you by us. You will have the ability to download and print documents we send to you through the DocuSign system during and immediately after the signing session and, if you elect to create a DocuSign account, you may access the documents for a limited period of time (usually 30 days) after such documents are first sent to you. After such time, if you wish for us to send you paper copies of any such documents from our office to you, you will be charged a \$0.00 per-page fee. You may request delivery of such paper copies from us by following the procedure described below.

Withdrawing your consent

[figure not shown]

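### SAP 8.2.5 reverses PROMIS Sleep Disturbance items 1, 2 and 8 without condition, although the protocol's form already prints them in reverse; on printed values they are reversed twice, and the stored coding is not stated.

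*SAP*

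**What the plan says.** SAP 8.2.5 covers the three PROMIS short forms together. Each has "8 items in which responses are scored 1 to 5 for each item"; the items are summed to a raw score, converted to a T-score (Appendix B for Sleep Disturbance), and the T-score is analysed. It then adds that "items 1, 2, and 8 of the PROMIS Sleep Disturbance Instrument will need to have their directionality reversed for calculating the totals".

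The form is reproduced in Protocol Appendix 7. Item 1 (overall sleep quality), item 2 ("My sleep was refreshing") and item 8 ("I was satisfied with my sleep") carry the printed values 5, 4, 3, 2, 1 from left to right. Items 3 to 7 carry 1, 2, 3, 4, 5.

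On data capture, the protocol gives only general rules. Table 2 has a footnote: "For telephone visits, the patient will be mailed all applicable patient reported outcomes for a given visit". Section 11.6.1 repeats it for Week 14: "all PROs should be mailed ahead of the visit and returned to the clinic after completion via courier". For data collected on paper, Section 17.4 requires that "the data must be entered into the CRF and verified that it has been transcribed correctly". Protocol 12.1.3 names the PROMIS scales but gives no scoring rule.

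**The concern.** The three items the SAP wants reversed are exactly those the form already prints in reverse. A programmer who takes the printed numbers as the item scores and then follows the SAP turns these items back, so they run against the other five. Nothing says whether the CRF field holds the printed number, the response label or the box position. At least some questionnaires are completed on paper, so the transcription convention matters, and the check on transcription does not define it.

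At stake are the Week 14 PROMIS Sleep Disturbance endpoint and its by-visit exploratory repeats. Wrong totals would still lie between 8 and 40, so a range check would pass. The error would act on both arms alike and could not create a difference where no item has a treatment effect. It would shrink an effect shared equally by all items, and could reverse the sign of one concentrated on items 1, 2 and 8.

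**Working it through.** **Inputs.** Printed item values: Protocol Appendix 7. Reversal rule: SAP 8.2.5, taken as 6 - x on a 1-to-5 item. Raw-to-T conversion: SAP Appendix B. The plan states no figure of its own to reproduce here. A lower T means less sleep disturbance.

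**1. Direction of the printed values.** On items 1, 2 and 8 the worst answer is printed 5 and the best 1. On items 3 to 7 the worst answer is also 5 and the best 1. The plain sum therefore runs from 8 (best) to 40 (worst), the range of Appendix B.

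**2. Same level v on every item, printed values stored.** Correct raw = 8v. Under the rule, raw = 5v + 3(6 - v) = 2v + 18.

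| v | Correct raw | Correct T | Rule raw | Rule T |
|---|---|---|---|---|
| 1 | 8 | 30.5 | 20 | 52.4 |
| 2 | 16 | 47.9 | 22 | 54.3 |
| 3 | 24 | 56.2 | 24 | 56.2 |
| 4 | 32 | 64.0 | 26 | 58.1 |
| 5 | 40 | 77.5 | 28 | 60.0 |

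The T span falls from 77.5 - 30.5 = 47.0 to 60.0 - 52.4 = 7.6.

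**3. One-step improvement on every item.** Correct change in T: -13.5 (5 to 4), -7.8 (4 to 3), -8.3 (3 to 2), -17.4 (2 to 1). Under the rule it is -1.9 at every step.

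**4. Improvement on some items only, starting at 4 throughout.**
- Items 1, 2 and 8 go to 3: correct raw 32 to 29, T 64.0 to 61.0, change -3.0. Rule: raw 26 to 29, T 58.1 to 61.0, change +2.9.
- The other five go to 3: correct raw 32 to 27, T 64.0 to 59.1, change -4.9. Rule: raw 26 to 21, T 58.1 to 53.4, change -4.7.

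**5. When the sign flips.** With mean improvement a on the five items and b on the three, the true raw improvement is 5a + 3b and the recorded one is 5a - 3b. The recorded sign is wrong when b > 5a/3 = 1.67a.

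**6. Illustration of lost effect size (assumed inputs).** Assume equal item variances, a common inter-item correlation r and the same treatment shift on every item. The raw-score shift falls from 8 units to 2. The variance of the sum goes from 8 + 56r to 8 + r(20 + 6 - 30) = 8 - 4r. The share of the standardised effect kept is (2/8) × √[(8 + 56r)/(8 - 4r)]: 0.477 at r = 0.3, 0.612 at r = 0.5 and 0.753 at r = 0.7. The documents give no value for r.

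**7. The other coding.** If left-to-right box position is stored, the best answer to items 1, 2 and 8 is 5 and the worst is 1. With the rule, all-best = 8 and all-worst = 40, which is correct. Without it, all-best = 3×5 + 5×1 = 20 and all-worst = 3×1 + 5×5 = 28, which is the same error.

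**The case against.** The best defence is that no error in the data has been shown. Patients mark a box, not a number, and the field may well hold box position. The Fatigue and Cognitive Function forms run 1 to 5 from left to right, so uniform position coding with one reversal note for Sleep Disturbance would be coherent. The note names exactly the positively worded items and has an evident purpose: to make all eight point the same way. It could even be read as describing the form's own reverse printing. Item code lists often sit in CRF annotations or programming specifications rather than in an SAP. The sign flip also needs an uneven pattern of improvement that nothing in the documents suggests.

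Much of this stands. The purpose of the note does fit box-position data, in which case nothing is lost. SAP Appendix E shows that specifications exist, since random seeds are to be "documented in the programming specifications and the programs themselves", but it says nothing about item scoring. What the defence does not supply is any statement of box-position coding. The instruction is worded as a step to be carried out, and on the only item values the documents print, carrying it out gives a wrong score. The planned summary statistics might reveal scores bunched near the middle of the scale, but that is not assured.

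**Conclusion.** The concern holds as a conflict between SAP 8.2.5 and Protocol Appendix 7, with the deciding fact, the stored coding, left unstated. It does not show that the analysis will be wrong. All the sizes above apply only if printed values are stored, and the shares of 48%, 61% and 75% of the standardised effect are illustrations under assumed correlations, not an expected loss.

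The point is minor. SAP 3.2.2 lists PROMIS Sleep Disturbance among the other secondary endpoints, and SAP 8.1.1.2 treats its p-values as descriptive. The primary endpoint, the three key secondaries (diary sleep quality, PROMIS Fatigue and PROMIS Cognitive Function) and the Insomnia Severity Index are not affected. Confidence is medium, because the annotated CRF and the programming specifications are not available here.

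**What to change.** Before database lock, read the stored coding off the annotated CRF and put the matching sentence in SAP 8.2.5.

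- If printed values are stored: *Each item is scored with the value printed on the Appendix 7 form, so that higher = worse for all eight items; no further reversal is applied.*
- If box position is stored: *Responses are stored as left-to-right box position; 6 - x is applied to items 1, 2 and 8, so that higher = worse for all eight items.*

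Then run two test records through the scoring program (all-best must give 8, all-worst 40), and check on blinded data that all eight scored items correlate positively with one another.

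Do not simply delete the present sentence: with box-position data, deletion would create the error it is meant to prevent. The cost is one look at the CRF, one SAP sentence, two test records and one blinded check.

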8.2.6 Patient Global Impression of Change (PGI-C)

PGI-C is a question completed by the patient at Weeks 2, 6, 10, and 14. The patient will rate the change in their Long COVID symptoms (specifically pain, sleep disturbance, fatigue, and/or

memory/concentration issues) on a 1-7 Likert scale, where 1 is “Very Much Improved” and 2 is “Much Improved”. Scores of 1 and 2 will be considered PGI-C responders, and all other scores will be considered non-responders for that visit. The proportion of responders in each treatment arm will be analyzed. Any missing PGI-C score will be considered a non-responder for that visit.

8.2.7 Post-COVID-19 Functional Status (PCFS) scale

The PCFS scale is an ordinal scale for assessment of patient-relevant functional limitations over time after COVID-19 infection.

The scale rates the functional status of patients as:

- 0 = No functional limitations
- 1 = Negligible functional limitations
- 2 = Slight functional limitations
- 3 = Moderate functional limitations
- 4 = Severe functional limitations
- D = Death

Missing values will not be imputed.

8.2.8 Insomnia Severity Index (ISI) – Patient version

The ISI is a 7-item self-reported questionnaire assessing the nature, severity, and impact of insomnia.

The usual recall period is the “last month” and the dimensions evaluated are severity of sleep onset, sleep maintenance and early morning awakening problems, sleep dissatisfaction, interference of sleep difficulties with daytime functioning, noticeability of sleep problems by others, and distress caused by the sleep difficulties.

The scores range from 0 (no problem) to 4 (very severe problem) yielding a total score ranging from 0 to 28. The total score is interpreted as:

- 0–7 = absence of insomnia
- 8–14 = sub-threshold insomnia
- 15–21 = moderate insomnia 22–
- 28 = severe insomnia

Missing items will be imputed with the average of the non-missing items, as long as at least 4 items are completed.

8.2.9 Epworth Sleepiness Scale (ESS)

The ESS is a self-administered questionnaire with 8 questions. The patient rates from 0 to 3 their usual chances of dozing off or falling asleep while engaged in 8 different activities. The total score can range from 0 to 24, with higher rating indicating higher average sleep propensity in daily life.

Missing items will be imputed with the average of the non-missing items, as long as at least 4 items are completed.

8.3 Safety Endpoints

To handle missing or partial AE and concomitant medication dates, the following rules will be applied.

For partial start dates:

1. If the year is unknown, then do not impute the date but assign a missing value.
2. If the month is unknown, then:
 - a. If the year matches the year of the first dose date, then impute the month and day of the first dose date.
 - b. Otherwise, assign “January.”
3. If the day is unknown, then:
 - a. If the month and year match the month and year of the first dose date, then impute the day of the first dose date.
 - b. Otherwise, assign “01.”

For partial end dates:

1. If the year is unknown, then do not impute the date but assign a missing value.
2. If the month is unknown, then assign “December.”
3. If the day is unknown, then assign the last day of the month.

Adverse events are categorized as pre-treatment adverse events or treatment-emergent adverse events based on the response to the CRF question “Did the AE start prior to the first dose?”

The missing severity of an AE will be imputed to “severe”; the missing relationship to study drug of an AE will be imputed to “possibly related”.

After implementing the rules above, the following strategy will be used to determine whether medications with missing start or stop dates are prior or concomitant medications:

1. If the start date and stop date are both missing, then the most conservative approach is taken and the medication is considered to be a concomitant treatment.
2. If the start date is missing but the stop date is not missing and is after the day of first study dose administration, then the most conservative approach is taken and the medication is considered to be concomitant.
3. If the start date is missing but the stop date is not missing and is on or before the day of first study dose and after the date of signed informed consent, then the medication is considered to be a prior treatment.
4. If the start date is not missing but the stop date is missing, then the most conservative approach is taken and the medication is considered to be concomitant.

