11.7. Visit 7 (Week 16/Post-study Safety Follow-up)

Visit 7 should occur approximately 2 weeks \pm 7 days after Visit 6/ET. This visit will be performed by telephone, to collect any additional data on concomitant medication and AEs and the general condition of the patient.

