12. MEDICATIONS

12.1 Concomitant Medication

All medications will be coded using a current version of the World Health Organization Drug Dictionary. Prior and concomitant medications will be summarized by treatment group and by the number and percentage of patients taking each medication, classified by using WHO-DD Anatomical Therapeutic Chemical Levels 1 and 3 and preferred term.

Prior medications are defined as medications or therapies initiated prior to the start of the study drug and terminated prior to the start of study drug. Hence, these medications or therapies will have end dates prior to the first dose date of study drug. Concomitant medications are defined as any medications other than the study drug that a patient receives concurrently with the study drug. These medications will have end dates on or after the first dose date of the study drug.

Prior and Concomitant medications will be summarized. All medications will be presented in a listing.

Please refer to [Section 8.3](#) to impute the partial start date and end date of concomitant medication.

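### The SAP's date rules for concomitant medication set no limit at the last dose, so drugs started after treatment can enter the by-arm concomitant table, against the SAP's own definition

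*SAP*

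**What the plan says.** **Definition (SAP 12.1).** Concomitant medications are "any medications other than the study drug that a patient receives concurrently with the study drug". The date criterion follows: "These medications will have end dates on or after the first dose date of the study drug". Prior medications are those that ended before the first dose date. No third category is defined.

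**Incomplete dates (SAP 8.3).** After partial dates have been imputed, four rules "determine whether medications with missing start or stop dates are prior or concomitant medications".
- Rule 1: both dates missing, concomitant.
- Rule 2: start missing and stop after the first-dose day, concomitant.
- Rule 3 reads: "If the start date is missing but the stop date is not missing and is on or before the day of first study dose"; if the stop is also after consent, prior.
- Rule 4: "If the start date is not missing but the stop date is missing, then the most conservative approach is taken", that is, concomitant.

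**Output (SAP 12.1).** "Prior and concomitant medications will be summarized by treatment group and by the number and percentage of patients taking each medication". All medications also go into a listing.

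**Data collection (Protocol 11.7 and 11.8, Table 2).** Visits 7 and 8 are telephone calls about 2 and 4 weeks after Visit 6 or early termination. Visit 7 is held "to collect any additional data on concomitant medication and AEs", and Visit 8 has the same purpose. Protocol 11.6.2 gives both calls to early terminators as well.

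**End of the ban (Protocol Synopsis and 7.1).** Excluded medications are barred only up to the Week 14 or early termination visit.

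**The concern.** The definition requires overlap with study drug. The date rules meant to implement it have a lower bound (first dose) but no upper bound (last dose). A programmer works from date rules, and these admit any medication that starts after treatment has ended.

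Such records are foreseeable. Some patients give up pain or sleep medication to enter the trial, the ban ends at Visit 6 or early termination, and medication recording continues for about four weeks more.

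What is at stake is how the by-arm medication table reads. SAP 10.1.1 analyses data as observed for all intercurrent events, so on-treatment use of drugs that affect pain or sleep can be judged only descriptively. A table that mixes on-treatment use with resumption afterwards could be misread as poor adherence to the restrictions, or as a difference between arms in rescue use.

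**Working it through.** The plan gives no figure on this point to reproduce. The check applies the stated date rules to example records and compares the result with actual overlap.

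**Inputs.** First dose is Day 1. The nominal last dose is Day 98 (Protocol Synopsis, dosing through Day 98). Visit 8 is Day 127 ± 7 (Protocol Table 2). The early-termination example uses a visit on Day 24, as in SAP 8.2.1, with the last dose assumed to be on Day 23.

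**Overlap test.** A record overlaps dosing if its start is on or before the last dose and its stop is on or after the first dose.

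| Record | Last dose | Class under the date rules | Overlaps dosing? | Class after the fix |
|---|---|---|---|---|
| Day -200 to Day -22 | 98 | prior (12.1) | no | prior |
| Day 40 to Day 50 | 98 | concomitant (12.1) | yes | concomitant |
| Day 100, no stop date | 98 | concomitant (rule 4) | no | post-treatment |
| Day 100 to Day 120 | 98 | concomitant (12.1) | no | post-treatment |
| Day 25, no stop date | 23 | concomitant (rule 4) | no | post-treatment |

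All three post-dose starts are classed as concomitant by the date rules, and none meets the definition. The fourth row has complete dates, so the gap is in the 12.1 date criterion as well as in the missing-date rule. The two records that started before the last dose keep their class.

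**Exposed window.**
- Completer: 127 − 98 = 29 days. With the Visit 8 window: 120 − 98 = 22 to 134 − 98 = 36 days.
- Early terminator: Visit 8 falls at about 24 + 28 = Day 52, so 52 − 23 = 29 days, again 22 to 36 with ± 7.

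The window has the same length in both cases but is a different share of the recorded days: 29/127 = 22.8% and 29/52 = 55.8%. These are shares of calendar days, not of patients or records.

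**Illustration under assumptions.** The documents give no rate of resumption. Let *u* be true on-treatment use of a drug and *r* the proportion of the remaining patients who start it after the last dose. The table would then show *u* + (1 − *u*)*r*.

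| | r = 5% | r = 10% | r = 20% | r = 30% |
|---|---|---|---|---|
| u = 5% | 9.75% | 14.5% | 24.0% | 33.5% |
| u = 10% | 14.5% | 19.0% | 28.0% | 37.0% |

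Both *u* and *r* are invented. The grid shows how the error behaves, not how large it will be.

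**First-dose-day boundary.** Take a medication with a missing start that stopped on the first-dose day. Rule 3 includes that day and says prior; 12.1 requires a prior medication to end before that day and so says concomitant. With the same stop date and a known start before Day 1, only 12.1 applies and the class is concomitant. The class then depends on whether a start date happened to be recorded.

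**The case against.** The strongest reply is that the definition already supplies the limit. A drug first taken after the last dose is not received concurrently with study drug, and the end-date sentence may be read as only separating concomitant from prior. Rule 4 is likewise a narrow missing-date rule. The documents also do not say whether an ongoing drug is stored as a missing stop date. This stands far enough that the miscount is a risk under literal programming, not a certainty. It does not remove the conflict: the date criterion is the operational text, it contradicts the definition for post-dose starts, and it does so even with complete dates.

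Four stronger readings are tempting, and the documents do not support them.
- *This is the only by-arm view of confounding treatment.* SAP 9.2 summarises protocol deviations by type and arm, which could capture prohibited drugs used on treatment. The medication table is the drug-level view, and permitted drugs that affect pain or sleep need not be deviations.
- *The table is certain to be wrong.* That depends on how it is programmed and on how many patients start drugs after the last dose. The listing of all medications lets post-dose starts be found wherever a start date is recorded, although it does not correct the table.
- *The opioid flag in SAP 12.2 is in error.* The flag identifies opioid records after review before database lock. It makes no claim about on-treatment use, and no by-arm opioid table is stated.
- *A large share of patients will be miscounted.* No resumption rate is given, and the protocol expects some patients to need no washout.

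The boundary conflict is real but trivial: it needs a missing start and a stop exactly on Day 1. As dosing begins at bedtime that day, calling such a drug prior is clinically defensible. The issue is only that two sections disagree.

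**Conclusion.** The point holds as a minor error in the rules as written. The date criterion in SAP 12.1 and rule 4 in 8.3 would class medications started after the last dose as concomitant, contrary to the definition in 12.1. The protocol collects such records over a nominal 29 days (22 to 36), after excluded drugs are no longer barred.

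The number of patients affected, and any difference between arms, cannot be derived from the documents. The affected output is a descriptive table. No efficacy analysis in the SAP uses the prior or concomitant class, so the primary and key secondary results do not change.

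The conclusion assumes that the table is programmed to the stated dates. The window figures assume a last dose on Day 98 for a completer and on Day 23 in the early-termination example.

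**What to change.** 1. In SAP 12.1 and in 8.3 rule 4, add that a known start date must be on or before the last dose date used in 12.3.
2. Report medications with a later start in a separate post-treatment category.
3. Leave records with a missing start date as concomitant. Rules 1 and 2 need no last-dose condition, because they apply only when there is no start date to compare.
4. Align the first-dose-day boundary with 12.1: in rule 3 change *on or before* to *before*, and in rule 2 change *after* to *on or after*.

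Some post-dose starts with partial dates will remain concomitant, because 8.3 imputes a start in the first-dose year or month to the first dose. That residue errs towards inclusion and can be footnoted.

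The cost is a few words in two SAP sections and one extra category in an existing table. No new data are needed, since 12.3 already uses the last dose date.
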